#### 5.2. General Methods

Unless otherwise specified, disposition, baseline, concomitant medications, study intervention exposure data, and safety data will be summarized by cohort and with both cohorts combined. Efficacy data will be summarized by cohort only.

#### 5.2.1. Data Handling After the Cutoff Date

Data after the cutoff date may not undergo the cleaning process and will not be displayed in any listings or used for summary statistics, statistical analyses or imputations except to derive last contact date.

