## 2. INTRODUCTION

This SAP provides the detailed methodology for summary and statistical analyses of the data collected in Study C1071003. This document may modify the plans outlined in the protocol; however, any major modifications of the primary endpoint definition or its analysis will also be reflected in a protocol amendment.

Any deviations from this analysis plan will be described in the Clinical Study Report (CSR).

This study has two cohorts: Cohort A will enroll participants who are naïve to BCMA-directed therapies, and Cohort B will enroll participants who have prior exposure to BCMA-directed therapies. The planned interim analysis and final analysis of the primary endpoint for the respective cohort will include all data up to a data cutoff date which will be determined by the criteria as outlined in Section 5.1. If a cohort is stopped at its interim analysis, this interim analysis will be considered the final analysis of the primary endpoint for the cohort. All summaries and analyses associated with a planned analysis will include all data pertaining to visits/assessments performed up to and including the data cutoff date in the respective cohort.

Additional analyses of the non-efficacy data may be performed for publication and review. Additional analyses of the efficacy data may be provided per regulatory agency request/agreement.

As this is an open-label non-randomized study, the treatment is unblinded on participant level. However, the aggregate/cumulative efficacy data summary by cohort should be unavailable to the study team and the external investigators until the database snapshot for the primary analysis.

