#### 5.2.7. Date of Last Contact

The date of last contact will be derived for participants not known to have died at the data cutoff date using the latest complete date (ie, imputed dates will not be used in the derivation) among the following:

- All assessment dates (eg, blood draws [laboratory, Pharmacokinetics (PK)], vital signs, physical exam, performance status, ECG, Echocardiograms [ECHO]/multigated acquisition [MUGA] scans, disease assessments, etc.);
- Start and stop dates of concomitant therapies including non-drug treatments or procedures;
- Completion dates for PRO Questionnaires;
- Start and end dates of new therapies administered after study intervention discontinuation including systemic therapy, radiation, and surgeries;
- AE start and end dates;
- Last date of contact collected on the 'Survival Status' CRF (do not use date of survival follow-up assessment unless status is 'alive');
- Study intervention start and end dates;
- Date of discontinuation on disposition CRF pages (do not use if reason for discontinuation is lost to follow-up or death).

Only dates associated with actual examinations of the participant will be used in the derivation. Dates associated with a technical operation unrelated to participant status such as the date a blood sample was processed or dates when data were entered into the CRF will not be used.

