#### 5.2.11. Nominal and Unscheduled Visits

For all algorithms and analyses, visit labels as specified on the CRF will be used as the nominal timepoint (ie, assessment will not be slotted).

Unless otherwise specified, unscheduled assessments will not be displayed in summary tables by nominal visit/timepoint. Unscheduled assessments will be used when deriving baseline and worst case on-treatment for safety and PRO analyses (except where noted for baseline ECGs). Additionally, unscheduled assessments will be used for efficacy analyses (eg, defining date of progression/censoring, best overall response, date of last contact).

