## 5.3.3.3. Date of Death

Missing or partial death dates will be imputed based on the last contact date:

- If the date is missing, it will be imputed as the day after the date of last contact;
- If the day or both day and month is missing, death will be imputed to the maximum of the full (non-imputed) day after the date of last contact and the following:
  - Missing day: 1st day of the month and year of death;
  - Missing day and month: January 1st of the year of death.

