## 5.3.3.4. Date of Start of New Anticancer Therapy

Incomplete dates for start date of new anticancer therapy (drug therapy, radiation with curative intent, transplant) will be imputed as follows and will be used for determining censoring dates for efficacy analyses and in the derivation of the end of the on-treatment period. PD date below refers to PD date by investigator assessment. If the imputation results in an end date prior to the imputed start date, then the imputed start date should be set to the end date.

- The end date of new anticancer therapy will be included in the imputations for start date of new anticancer therapy. If the end date of new anticancer therapy is
  - completely missing then it will be ignored in the imputations below;
  - partially missing with only year (YYYY) available then the imputations below will consider 31DECYYYY as the end date of the new anticancer therapy;
  - partially missing with only month and year available then the imputations below will consider the last day of the month for MMMYYYY as the end date of the new anticancer therapy.
- For participants who have not discontinued study intervention at the analysis cutoff date, last dose of study treatment is set to the analysis cutoff date in the imputations below.
- If the start date of new anticancer therapy is completely or partially missing, then the imputed start date of new anticancer therapy is derived as follows:
  - Start date of new anticancer therapy is completely missing
    - Imputed start date = min [max(PD date + 1, last dose of study intervention + 1), end date of new anticancer therapy]
  - Only year (YYYY) for start of anticancer therapy is available
    - IF YYYY < Year of min [max(PD date + 1, last dose of study intervention + 1), end date of new anticancer therapy]

THEN imputed start date = 31DECYYYY;

• ELSE IF YYYY = Year of min [max(PD date + 1, last dose of study intervention + 1), end date of new anticancer therapy]

THEN imputed start date = min [max(PD date + 1, last dose of study intervention + 1), end date of new anticancer therapy]

• ELSE IF YYYY > Year of min [max(PD date + 1, last dose of study intervention + 1), end date of new anticancer therapy]

THEN imputed start date = 01JANYYYY

- Both Year (YYYY) and Month (MMM) for start of anticancer therapy are available
  - IF YYYY = Year of min [max(PD date + 1, last dose of study intervention + 1), end date of new anticancer therapy], AND

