# 6.2.7. Overall Survival

OS is defined as the time from the date of first dose until death due to any cause and will be calculated in months as follows:

OS (months) = [date of death or censoring - date of first dose +1] / 30.4375

Survival status is expected to be collected irrespective of study intervention discontinuation or participant's request to discontinue study procedures. All participants who have not withdrawn consent for further participation in the study should be followed for survival until the end of the study. OS for participants not known to have died are censored on the date of last known alive.

OS time will be estimated using the same Kaplan-Meier method and displayed graphically as described for PFS in Section 6.2.4. Median OS and 2-sided 95% CI will be provided. The OS rate at 12, 24, and 36 months (and in subsequent 12-month increments while there are participants still at risk) will be estimated with corresponding two-sided 95% CIs.

Frequency (number and percentage) of participants with death events and censoring reasons will be presented by cohort along with the overall event and censor rates. The event and censoring reasons are as follows:

- Death;
- Ongoing and no death;
- Withdrawal of consent;
- Lost to follow-up.

The OS time or censoring time and the reasons for censoring will also be presented in a listing.

In addition, duration of follow-up time will be summarized with simple descriptive statistics, as well as with reverse Kaplan-Meier method.

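### SAP 5.2.1 lets post-cutoff data set the last contact date, and no rule caps OS censoring at the data cutoff; if that date is the OS censoring date, follow-up is added in which deaths cannot count (minor)

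*SAP*

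**What the plan says.** Four parts of the SAP bear on this.

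- **Section 2** sets the general rule: summaries and analyses tied to a planned analysis "will include all data pertaining to visits/assessments performed up to and including the data cutoff date".
- **Section 5.2.1** makes one exception. Data after the cutoff "will not be displayed in any listings or used for summary statistics, statistical analyses or imputations except to derive last contact date".
- **Section 5.2.7** says the date of last contact is "derived for participants not known to have died at the data cutoff date using the latest complete date" over a list of sources. The cutoff here selects who receives the date. It does not limit how late the date may be.
- **Section 6.2.7** gives the censoring rule: "OS for participants not known to have died are censored on the date of last known alive". Protocol 9.4.3.1 has the same rule. Neither document defines the term or ties it to the cutoff. Section 6.2.7 also plans a reverse Kaplan-Meier summary of follow-up.

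Elsewhere the SAP does name the cutoff in a date rule. In Section 5.3.3.4, for participants still on treatment, "last dose of study treatment is set to the analysis cutoff date in the imputations below". Section 5.3.3.2 similarly uses the cutoff as the last dosing date for ongoing participants. The OS rule has no such sentence.

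**The concern.** Censoring is harmless when a participant contributes time at risk only over a period in which a death would have been counted. Under 5.2.1, a contact with a living participant after the cutoff is usable, but a death after the cutoff is not. If the first feeds the OS censoring date, survivors stay in the risk set past the cutoff, over a stretch in which the event count is zero by construction. The events are the same and the risk sets are as large or larger. So the Kaplan-Meier curve can only rise, and the reverse Kaplan-Meier follow-up can only lengthen, compared with stopping at the cutoff.

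At stake are the OS curve, the OS rates at fixed times and the reported follow-up. Two programmers could also resolve the undefined term differently.

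**Working it through.** **Is the last-known-alive date the 5.2.7 date?** The SAP does not say so. Three things point that way:

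1. Both rules cover participants not known to have died.
2. For the survival status form, 5.2.7 tells the programmer "do not use date of survival follow-up assessment unless status is" alive, a condition that fits a date used to show survival.
3. Section 5.2.11 says "unscheduled assessments will be used for efficacy analyses (eg, defining date of progression/censoring, best overall response, date of last contact".

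Section 5.2.7 is also the only derivation of such a date. Against this, the last contact date has another stated use, imputing a missing death date: "it will be imputed as the day after the date of last contact" (5.3.3.3). So the link is a reasonable inference and no more.

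**Size on that inference.** The documents give no OS assumption, so there is no plan figure to reproduce.

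Inputs from the documents:
- OS rate at 12 months (SAP 6.2.7).
- Earliest final analysis after two post-baseline assessments (SAP 5.1.2). At 28-day intervals that is about 2 months after last entry.

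Assumed, not in the documents:
- Uniform accrual over 11 months.
- Exponential OS with median M of 12 to 24 months.
- Contact running w = 1 to 3 months past the cutoff.
- Complete contact, except where stated.

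Let m be the months from last entry to cutoff, and G(t) the share of participants whose first dose was at least t months before the cutoff. Then G(t) = 1 for t ≤ m and (m + 11 − t)/11 after that. At time t, deaths are counted only in the share G(t), but the risk set holds the share G(t − w). The estimated hazard is therefore the true hazard times G(t)/G(t − w). With E the integral of G(t)/G(t − w) from 0 to 12, the estimated 12-month rate is 2^(−E/M), against a true 2^(−12/M).

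- m = 9, w = 1: E = 9 + 10.5/11 + (2 − ln(11/9)) = 9 + 0.955 + 1.799 = 11.754
- m = 9, w = 3: E = 9 + 28.5/11 = 11.591
- m = 2, w = 1: E = 2 + 10.5/11 + (9 − ln(11/2)) = 2 + 0.955 + 7.295 = 10.250
- m = 2, w = 3: E = 2 + 28.5/11 + (7 − 3 ln(11/4)) = 2 + 2.591 + 3.965 = 8.556
- m = 12: G = 1 throughout, so E = 12

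| Cutoff after last entry | M = 12 (true 50.0%) | M = 24 (true 70.7%) | Range of error, points |
|---|---|---|---|
| 2 months | 55.3 to 61.0 | 74.4 to 78.1 | +3.7 to +11.0 |
| 9 months | 50.7 to 51.2 | 71.2 to 71.5 | +0.5 to +1.2 |
| 12 months | 50.0 | 70.7 | 0 |

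Large-sample simulation agrees to within about 0.2 points. With censoring capped at the cutoff, the error under complete contact is within 0.2 points of zero. Median reverse Kaplan-Meier follow-up lengthens by 0.8 to 2.6 months uncapped.

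**Sparse contact.** Suppose instead that every participant is contacted only every 3 months. Simulated error in the 12-month rate, in points:

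| Cutoff, lag | Uncapped | Capped |
|---|---|---|
| 2 months, lag 1 | −4.0 to −2.9 | −5.8 to −4.2 |
| 2 months, lag 3 | +4.6 to +6.4 | −0.7 to −0.2 |
| 9 months, lags 1 to 3 | −0.7 to +0.8 | −0.9 to +0.1 |

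At lag 1, about 67% of those alive at the cutoff have no later contact. They are censored at their last earlier contact, while deaths up to the cutoff all count, and that pulls the curve down.

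**The case against.** The case against has four parts.

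- **The key step is inferred.** Neither document equates the two dates, and 5.2.11 concerns unscheduled visits and does not mention OS. This stands, and the point is conditional for that reason. If the inference is wrong, the censoring date has no derivation at all, and a definition is still needed.
- **Section 2 already stops analyses at the cutoff.** The 5.2.1 exception may exist only to confirm that a participant was alive then. That reading is plausible, but it is not written. A reader might go the other way and say the SAP contradicts itself. It does not: 5.2.1 is an express exception to a general rule. What is missing is a statement of how the two fit together.
- **The large figures need an unlikely cutoff.** A reader might take 11 points as the expected bias. Enrollment closed in January 2022 (Protocol 9.2), so a 2-month cutoff falls around March 2022. SAP version 9, dated 26 October 2022, still clarifies the final efficacy analysis. A cutoff can precede a SAP date, so this is not proof, but it makes the earliest cutoff improbable. The objection stands.
- **The bias need not be upward, and the cap need not help.** Relative to a capped rule the curve can only rise. Relative to true OS, the sparse-contact case shows a downward error, and there the cap alone moves further from the truth. This stands too. Three-monthly contact for everyone is harsher than the schedule, which has weekly or two-weekly dosing visits and assessments at least every 4 weeks after stopping without progression (Protocol 6.1.1 and 7.1).

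A reader might also extend the concern to the planned 36-month rate at study end. Protocol 4.4 ends the study once all participants have 2 years of OS follow-up. An effect at that cutoff would need contact after the study has ended, which the documents do not provide for, so no size is claimed.

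**Conclusion.** The concern holds in conditional form. The 5.2.1 exception, the untruncated date in 5.2.7 and the undefined, uncapped censoring date in 6.2.7 are all in the text; the link between the last two is inferred. On that link, OS and its follow-up summary gain post-cutoff time in which deaths are not counted.

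Under the stated assumptions and complete contact, the 12-month rate is overstated by about 1 point at a 9-month cutoff. The sampling SD there (median OS 18 months) is 4.4 points for 123 participants and about 6 for 64. Any planned rate is unaffected once every participant has that much follow-up by the cutoff. The documents give neither the actual cutoff nor the lag, so they do not support saying that reported OS is inflated, or by how much.

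Severity is minor. OS is a descriptive secondary endpoint with no test. ORR does not use this date, and PFS, DOR and DOCR censor at the last adequate disease assessment.

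**What to change.** 1. In SAP 5.2.7 and 6.2.7, state that the last-known-alive date is the 5.2.7 date, and that OS is censored at min(that date, data cutoff date).
2. Keep the 5.2.1 exception but reword it: a contact or death record after the cutoff serves only to show that the participant was alive at the cutoff, and such participants are censored at the cutoff.
3. In the OS table, report how many participants have no contact on or after the cutoff.

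Item 3 is needed because items 1 and 2 do not repair sparse contact. With 3-monthly contact and a 2-month cutoff, counting later death records as proof of life brings the capped error to −0.1 to 0.0 points at a 3-month lag, but leaves it at −5.2 to −3.9 at a 1-month lag.

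The cost is two or three sentences, one line of code and one count. At an early cutoff, OS will read lower than under the uncapped rule.

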#### 5.2.2. Pooling of Centers

In order to provide overall estimates of treatment effects, data will be pooled across centers. The 'center' factor will not be considered in statistical models or for subgroup analyses due to the high number of participating centers in contrast to the anticipated small number of participants enrolled at each center.

#### 5.2.3. Analyses to Assess the Impact of COVID-19 Pandemic

The study enrollment may start during the COVID-19 pandemic period. If so, data summaries and analyses may be performed to assess the impact of COVID-19 on the trial population and study data. Details of these summaries and analyses are included in the respective sections.

## 5.2.4. Definition of Study Day

The study day for assessments occurring on or after the first dose of study intervention (eg, adverse event onset, tumor measurement) will be calculated as:

Study day = Date of the assessment/event - start date of study intervention + 1.

The study day for assessments occurring prior to the first dose of study intervention (eg, baseline characteristics, medical history) will be negative and calculated as:

Study day = Date of the assessment/event - start date of study intervention.

The study day will be displayed in all relevant data listings.

### 5.2.5. Definition of Cycle and Cycle Day

Cycle start and end dates are derived per participant. The definition for each cycle is driven by study drug elranatamab. Elranatamab is administered on Days 1, 8, 15 and 22 of each 28-day cycle. As described in Protocol Section 6.1.1, if a participant has received QW dosing for at least 6 cycles and has achieved an IMWG response category of PR or better persisting for at least 2 months, the dosing interval will be changed from QW to Q2W. If the participant subsequently begins to have an increase of disease burden not yet qualifying as PD according to IMWG criteria, dose intervals should return to weekly dosing. If the dose interval is changed, cycles should remain the same length (ie, 4-week cycles). In either dosing scenario, the nominal cycle length is 28 days.

- For Cycle 1, the actual cycle starts date is the date each participant receives the first non-zero study intervention;
- For all other cycles, the actual cycle start date for each participant is the earliest start date of dosing in the Cycle X Day 1 visit CRF exposure page;
- For all but the last cycle;
  - Actual cycle stop date is calculated as the start date of the next cycle minus 1 day;
  - Actual cycle duration is calculated from Day 1 of a cycle to the day prior to Day 1 of the next cycle, as follows:

Actual Cycle Duration (weeks) = (cycle stop date – cycle start date + 1)/7

• For the last cycle, actual cycle duration is based on the actual cycle stop date which is last zero/non-zero dose date + (7 days if on QW or 14 days if on Q2W) – 1 day. If C1D4 is the last visit, cycle stop date is Day 7 if C1D4 occurred by then.

The cycle day will be calculated as:

Cycle day = Date of the assessment/event – cycle start date + 1.

## 5.2.6. Definition of Start of New Anticancer Therapy

Start date of new anticancer therapy (drug, radiation with curative intent, transplant) is used to determine the end of the on-treatment period (see Section 3.5) and for censoring in efficacy analyses (see Section 6.1).

The start date of new anticancer therapy is the earliest date after first dose date amongst the following:

- Start date of anticancer drug therapy recorded in the 'Next Anticancer Therapy (NXT CNCR)' eCRF pages;
- Start date of radiation therapy recorded in 'Concomitant Radiation' and 'Non-drug Treatments (NXT RAD)' eCRF pages;
- Start date of transplant recorded in 'Transplant details (TRANSPLT)' eCRF page.

When start date of anticancer therapy is missing or partially missing, the imputation rules described in Section 5.3.3.4 should be applied using the data collected on the eCRF pages described above.

#### 5.2.7. Date of Last Contact

The date of last contact will be derived for participants not known to have died at the data cutoff date using the latest complete date (ie, imputed dates will not be used in the derivation) among the following:

- All assessment dates (eg, blood draws [laboratory, Pharmacokinetics (PK)], vital signs, physical exam, performance status, ECG, Echocardiograms [ECHO]/multigated acquisition [MUGA] scans, disease assessments, etc.);
- Start and stop dates of concomitant therapies including non-drug treatments or procedures;
- Completion dates for PRO Questionnaires;
- Start and end dates of new therapies administered after study intervention discontinuation including systemic therapy, radiation, and surgeries;
- AE start and end dates;
- Last date of contact collected on the 'Survival Status' CRF (do not use date of survival follow-up assessment unless status is 'alive');
- Study intervention start and end dates;
- Date of discontinuation on disposition CRF pages (do not use if reason for discontinuation is lost to follow-up or death).

Only dates associated with actual examinations of the participant will be used in the derivation. Dates associated with a technical operation unrelated to participant status such as the date a blood sample was processed or dates when data were entered into the CRF will not be used.

#### 5.2.8. Disease Assessment Date

The Date of Disease Assessment at each nominal timepoint as provided by the investigator on the IMWG response CRF page and by BICR will be utilized for the respective analyses.

#### 5.2.9. Adequate Baseline Disease Assessment

Adequate baseline is defined using the following criteria:

- All documented lesions must have non-missing assessments (ie, non-missing measurements for target lesions and meeting criteria for measurable lesions, and non-missing lesions status at baseline for non-target lesions);
- Baseline lesions must be assessed with an acceptable method of tumor assessment as specified in the protocol (eg, PET/CT, CT or MRI);
- Measurable disease based on IMWG criteria as defined by at least 1 of the following:
  - Serum M-protein  $\geq 0.5$  g/dL by SPEP;
  - Urinary M-protein excretion  $\geq$ 200 mg/24 hours by UPEP;
  - Serum immunoglobulin FLC ≥10 mg/dL (≥100 mg/L) and abnormal serum immunoglobulin kappa to lambda FLC ratio (<0.26 or >1.65).

